3.2 Conditions for Patient Ineligibility

3.2.1 Direct evidence of regional or distant metastases after PET and surgical staging studies, or synchronous primary malignancy or prior invasive malignancy in the past 3 years, with the following exceptions:

- carcinoma in situ;
- early stage skin cancer that has been definitively treated;
- when an invasive malignancy has been treated definitively and the patient has remained disease free for ≥ 3 years;

3.2.2 Primary tumors >3 cm;

3.2.3 Prior systemic chemotherapy or thoracic surgery involving lobectomy or pneumonectomy;

3.2.4 Prior radiotherapy to the region of the study cancer that would result in overlap of radiation therapy fields;

3.2.5 Pure bronchioloalveolar carcinoma subtype of non-small cell lung cancer;

3.2.6 Active systemic, pulmonary, or pleural pericardial infection;

3.2.7 Pregnancy or women of childbearing potential and men who are sexually active and not willing/able to use medically acceptable forms of contraception; this exclusion is necessary because the treatment involved in this study may be significantly teratogenic.

4.0 PRETREATMENT EVALUATIONS/MANAGEMENT

NOTE: This section lists baseline evaluations needed before the initiation of protocol treatment that do not affect eligibility.

4.1 Required Evaluations/Management

4.1.1 EBUS is required within 4 weeks prior to treatment if there are suspicious nodes on the CT or PET/CT scan and/or if there was no prior mediastinoscopy. Patients who already have had mediastinoscopy, chamberlain procedure, or VATS are eligible for this trial if they meet the eligibility criteria.

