5.4 Registration

5.4.1 Summary of Procedures

This study incorporates a two-step registration process.

All patients can be registered after completing the Eligibility Checklist, STEP 1 via online registration; see the text below for online registration instructions.

All patients must be staged by FDG-PET/CT to confirm T1N0 disease. At this point, patients with confirmed T1N0 disease may be randomized.

Note: Sites must complete the Eligibility Checklist, STEP 2 via online registration for ALL patients, even for patients found not to have T1N0 disease, to indicate whether or not patients are able to continue protocol treatment and if not, to specify the reason.

Patients found not to have T1N0 disease on PET/CT will be treated off study per standard of care and will not be followed.

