6.0 RADIATION THERAPY

Note: All participating institutions will be credentialed for a dry-run case, phantom irradiation, IGRT, and 3DCRT (or IMRT, if used) as described in Section 5.1 prior to registering patients to the study. Centers not credentialed for IMRT are not permitted to enroll and treat patients with this approach.

Protocol treatment must begin within 14 calendar days after randomization.

The protocol procedures associated with SBRT will respect updated guidelines set by ACR/ASTRO [182].

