APPENDIX II: STUDY PARAMETER TABLE: *See section 11.1 for details and exceptions

Assessments	Within 6 wks prior to registration, unless otherwise noted	Arm 1				Arm 2				Both Arms
		Prior to surgery in clinic OR Pre-Op OR prior to surg.remove of tumor	Intra-Op after surgical removal of tumor	Prior to dis-charge	4-6 wks Post-Op	Prior to 1st fraction of SBRT	After 3 rd fraction of SBRT	After all SBRT (the last day)	4-6 weeks after end of SBRT	
History & Physical	X				X				X	X
Thoracic Surgeon evaluation	X									
Document weight	X				X				X	X
Performance Score	X				X				X	X
PFTs (with DLCO)	X									X*
FDG-PET/CT scan	Within 4 wks				X					At 3, 12, 24 mos.
CT of chest/upper abdomen, with contrast	Within 4 wks				X					Chest CT with contrast at 3,6,9, 12, 18, 24, 36 mos.
EBUS	Within 4 wks prior to treatment									
Adverse event assessment					X			X	X	X
Pregnancy test, if applicable	Within 72 hrs.									
†Blood for research		X	X	X	X	X	X	X	X	
†Tissue for banking	For Both Arms: prior to treatment									

†For patients who consent to participate in the specimen banking component of the study; see Appendix I.

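### EBUS nodal staging is timed to treatment, not randomisation, so a result that should exclude a patient can first appear after allocation

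*Combined protocol and SAP*

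**What the plan says.** All references are to the combined protocol and SAP.

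- **Trigger and timing.** Section 4.1.1: "EBUS is required within 4 weeks prior to treatment if there are suspicious nodes on the CT or PET/CT scan", continuing "and/or if there was no prior mediastinoscopy". The EBUS row of Appendix II reads "Within 4 wks prior to treatment", although its column is headed by reference to registration.
- **Status.** Section 4.0 describes what follows as "baseline evaluations needed before the initiation of protocol treatment that do not affect eligibility".
- **Condition for randomisation.** Section 5.4.1: "All patients must be staged by FDG-PET/CT to confirm T1N0 disease. At this point, patients with confirmed T1N0 disease may be randomized". EBUS is not named.
- **Interval.** Section 6.0: "Protocol treatment must begin within 14 calendar days after randomization".
- **Biopsy before entry.** Section 3.1.2 requires negative biopsies of nodes that are over 1 cm or abnormal on PET, or else six months without change. Nodes of 1 cm or less without abnormal uptake count as N0 with no biopsy.
- **Exclusion.** Section 3.2.1 makes a patient ineligible on "Direct evidence of regional or distant metastases after PET and surgical staging studies".
- **Endpoint.** Sections 11.2.2 and 13.1.1 count nodal disease as local-regional failure.

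**The concern.** A nodal biopsy result bears directly on a stated exclusion, yet the plan classes the test as irrelevant to eligibility and lets it follow randomisation. A baseline exclusion can then become a post-randomisation event. Treatment allocation is known by that point, because surgery against radiotherapy cannot be masked. Whether such a patient is removed, switched or kept would be decided with the arm in view, and that decision touches the nodal component of the primary endpoint.

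The documents give an uneven basis for the decision. Section 8.1.5, in the surgery chapter, sets out a pathway for unexpected N1 or N2 disease. Section 6, the SBRT chapter, has no rule for a positive EBUS, and Section 6.1.5 confines the target to the primary tumour. Section 13 does not say how patients found node-positive after allocation are analysed.

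**Working it through.** **1. Where the EBUS window can fall.** Four weeks is 28 days (4.1.1, Appendix II). Let treatment start T days after randomisation, with T from 0 to 14. That limit stands in the radiation chapter but is worded for protocol treatment generally, so I apply it to both arms. The window runs from day T − 28 to day T, so the share after randomisation is T/28:

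- T = 0: 0%
- T = 7: 7/28 = 25%
- T = 14: 14/28 = 50%

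**2. Which patients can reach a first positive result after randomisation.**

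| Group | Biopsy forced before entry (3.1.2)? | EBUS required (4.1.1)? | Late first positive possible? |
|---|---|---|---|
| Enlarged or PET-abnormal nodes, all biopsied negative | Yes | Yes | Largely closed |
| Abnormal nodes, stable for 6 months | No | Yes | Yes under 3.1.2; Step 1 checklist item 3 omits the stability option |
| Imaging-N0, no prior mediastinoscopy | No | Yes, on the plain reading of and/or | Yes |
| Imaging-N0, prior mediastinoscopy | No | No | No |

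**3. Whether another check closes the gap.** Step 1 checklist item 12 asks for the studies in Section 3.0, and EBUS sits in Section 4. The Step 2 form offers N+ as a reason not to continue, but nothing requires an EBUS result by then.

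**4. The plan's own sample size.** Section 13.3 gives 90% against 75%, power 0.80 and error 0.20. With a one-sided pooled two-proportion formula and z = 0.8416:

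n = [z√(2 × 0.825 × 0.175) + z√(0.90 × 0.10 + 0.75 × 0.25)]² / 0.15² = [0.8416 × (0.5374 + 0.5268)]² / 0.0225 = 35.6, so 36 per arm and 72 in total.

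The 5% inflation gives 72 × 1.05 = 75.6, so 76. The figures reproduce, and the allowance is 76 − 72 = 4 patients for all ineligibility and attrition.

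**5. How many patients.** The documents give no EBUS-positive rate f, so 3% to 10% is an assumption.

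- Ceiling, if all 76 need EBUS: 76 × 0.03 = 2.3 to 76 × 0.10 = 7.6, about 2 to 8.
- If appointments are spread evenly over the window and treatment starts on day 14, half follow randomisation: 1.1 to 3.8.
- If every positive were found late and dropped, the chance that this alone exceeds the 4-patient allowance, P(X ≥ 5) with X binomial (76, f), is 0.33 at f = 5% and 0.89 at f = 10%.

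**6. Direction of bias.**

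*Removing patients.* With 36 in an arm at 90% control (32.4 controlled), dropping one who would have failed gives 32.4/35 = 92.6%, up 2.6 points. Dropping one who would have been controlled gives 31.4/35 = 89.7%, down 0.3.

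*Keeping patients.* Assume true control of 90% in both arms, positives failing after SBRT with probability g, the surgical arm unaffected, and a one-sided 0.20 non-inferiority test with 36 per arm (power 0.90 with no positives). SBRT control is 0.90(1 − f) + f(1 − g).

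| f | g | SBRT control | Power |
|---|---|---|---|
| 5% | 0.5 | 88.0% | 0.82 |
| 5% | 1 | 85.5% | 0.70 |
| 10% | 0.5 | 86.0% | 0.73 |
| 10% | 1 | 81.0% | 0.46 |

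These rows put the full f in the SBRT arm, so they are ceilings for illustration.

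**The case against.** The strongest reply is that the gap is narrow. Section 3.1.2 and Step 1 checklist item 3 already require negative biopsies of suspicious nodes, so the first EBUS trigger adds little risk. The second could be read as suspicious nodes in a patient without mediastinoscopy. That fits better with Section 3.1.2, which ties biopsy to visible nodes. On that reading the open route shrinks mainly to patients admitted on nodal stability. This stands as a limit: the wider route depends on the plain reading of and/or.

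Second, a reader might infer that EBUS-positive patients would leave the SBRT arm while those in the surgical arm would be resected and counted. The documents do not say so. Section 3.2.1 applies to both arms. Section 9.1.1 offers chemotherapy for unexpected pathologic stage II or III disease without naming an arm, and its caution about radiation lung injury suggests it has irradiated patients in mind. Section 11.3 continues follow-up whichever treatment stops. Different handling is therefore only a possibility left open by the surgery-only pathway.

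Third, Section 13.3 allows for some ineligible patients, Section 13.5.4 expects 95% to remain eligible on review, and sites may schedule EBUS early in practice. The allowance covers the lower part of the assumed range. It replaces lost numbers, however, and does not prevent selection after allocation; nor does the protocol require early scheduling.

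**Conclusion.** The point holds as a sequencing and consistency defect. A mandated nodal test that bears on Section 3.2.1 may be read for the first time after randomisation, while Section 4.0 says it does not affect eligibility. The ceiling is about 2 to 8 of 76 patients, resting on an assumed 3% to 10% positivity and on EBUS being needed by everyone. The number found late is smaller if appointments are spread over the window, of which at most 14 of 28 days follow randomisation.

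The net direction is unknown: removing node-positive patients from SBRT would favour SBRT, and keeping them would penalise it. A reader might count each such patient as 1/36, or 2.8 points, of the 15-point margin. That is not the bias per patient, which depends on the outcome the patient would have had and on whether the patient is removed or kept. Nor does the point make the stated sample size wrong. Confidence is medium, and the change is worth making because it is cheap.

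**What to change.** Where Section 4.1.1 already requires EBUS, require its result before Step 2 randomisation. Amend Section 5.4.1, the Step 2 checklist and the EBUS timing in Appendix II accordingly. Step 2 is the right place, since the Section 3.1.5 work-up is timed to registration. Record positives under the existing N+ reason, and take EBUS out of the Section 4.0 note on eligibility. Reconcile Sections 3.1.2 and 3.2.1 with the and/or trigger in Section 4.1.1, so that it is clear which patients need the test and what a positive result means for eligibility.

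The cost is protocol wording, some EBUS appointments moved earlier, and possibly a few days' delay to randomisation. It adds no procedure, patients or treatment rule. It does not remove nodal disease first found at resection, which belongs to the comparison itself: Section 13.3 already attributes the expected SBRT deficit largely to the absence of nodal dissection.

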5.0 REGISTRATION PROCEDURES

Note: This is a limited institution study.

5.1 Regulatory Pre-Registration Requirements (6/6/2013)

5.1.1 Prior to the recruitment of a patient for this study, investigators at participating institutions must obtain IRB/REC approval for this protocol, and submit IRB/REC approval and supporting documentation to the RTOG Headquarters ([contact]) or e-mail them to [contact].

The following documents also are required:

- Site contract;
- RT Credentialing (see Section 5.2 for details)
- Surgeon credentialing (see Section 5.3 for details)
- FDA 1572 (Investigator's agreement to follow FDA regulations and comply with the protocol)
- Investigator's current CV
- Investigator's completion of the American College of Radiology's Conflict of Interest form. This document can be found on the RTOG website:
<http://www.rtog.org/Researchers/PoliciesManuals/ConflictofInterestPolicy.aspx>
- Documentation of investigator's completion of Human Subject Protection Training (information about the National Institutes of Health (NCI) training can be accessed at <http://grants.nih.gov/grants/policy/hs/training.htm>; comparable training is acceptable);
- IRB/REC initial approval letter, annual continuing review approvals, and approvals of each amendment of the protocol;
- IRB/REC approved consent (English and native language versions*); *Note: Institutions must provide certification/verification of IRB/REB consent translation to RTOG Headquarters (described below);
- All Regulatory submissions must also include a completed IRB certification Form as a cover sheet, with the following information documented on the form:
 - Site NCI code;
 - Investigator's CTEP ID, if available;
 - IRB/REC registration number;
 - FWA number.

5.1.1.1 Translation of documents is critical. The institution is responsible for all translation costs. All regulatory documents, including the IRB/REC approved consent, must be provided in English and in the native language. Certification of the translation is optimal but due to the prohibitive costs involved RTOG will accept, at a minimum, a verified translation. A verified translation consists of the actual REC approved consent document in English and in the native language, along with a cover letter on organizational/letterhead stationery that includes the professional title, credentials, and signature of the translator as well as signed documentation of the review and verification of the translation by a neutral third party. The professional title and credentials of the neutral third party translator must be specified as well.

5.2 Pre-Registration Requirement: RT Credentialing (6-AUG-2018)

5.2.1 For participating institutions from China, a specific credentialing process will be arranged by a Medical Physics Co-Chair, [name] [name], or [name], prior to registration of patients.

Since the participating Chinese institutions have not completed the RTOG membership application process, a special credentialing document has been created that combines requirements from the RTOG membership application, American College of Radiology (ACR) practice guidelines, and specific benchmark credentialing for special procedures, such as downloadable tests from the American Association of Physics in Medicine (AAPM) Task Group 119 (www.aapm.org). This credentialing document is available to participating sites on the RTOG web site, www.rtog.org, under RTOG Foundation Study 3502.

The credentialing process for this study is distinctively different from the standard RTOG procedure in that a comprehensive review similar to that of ACR accreditation is performed by the Medical Physics Co-Chairs or their designees at each participating institution. The institution is required to prepare the documents specified in the credentialing document (summarized in Section 5.2.5 below) and have them ready for an onsite visit. More than one visit and/or follow-up submission of documentation may be needed for the completion of the credentialing. A phantom study with the MD Anderson Dosimetry Lab (MDADL) must be successfully completed. Close interactions between the Medical Physics Co-Chairs and participating institutions are necessary for this pioneering trial.

A summary of the credentialing requirements is provided below in Table 5.2 and in Sections 5.2.2 to 5.2.5. It is mandatory for institutions to complete the credentialing document (on the RTOG web site under RTOG Foundation Study 3502) to confirm that the institution has fulfilled all requirements. Institutions must have the completed questionnaire and requested data on site for review by the visiting Medical Physics Co-Chair, [name] [name], or [name], who will initial each page, sign the document, and deliver it to RTOG Headquarters for filing/storage.

Table 5.2

Summary of Radiation Therapy Quality Assurance Credentialing Requirements		
Components	Document & Data for Onsite Visit	Document & Data Submission
Facility Information	√	
Delivery System(s) and QA	√	
Planning System(s) and QA	√	
Policy and Procedure(s)	√	
Treatment & Other Records	√	
IGRT (including 4D imaging)	√	
Motion Management	√	
IMRT	√	
3D-CRT	√	
Dry-Run Case		√
Phantom irradiation		√

5.2.2 The delivery system for participating institutions includes a linear accelerator which can produce 6MV photon beams. An in-room IGRT system should be available using 3D (kV or MV Cone-beam CT or CT on-rail system) images, for localization and verification purposes. CyberKnife and Tomotherapy units, or equivalent, also are allowed if proper motion management is implemented and credentialled by Medical Physics Co-Chair. The quality assurance program should be implemented following TG 142 or equivalent, including the supplemental information in TG 142, as judged by visiting Medical Physics Co-chair.

5.2.3 The treatment planning system should have a 3D inhomogeneity dose calculation method. Convolution/superposition algorithms are required for this protocol. Monte Carlo calculation algorithms are also allowed. Acceptance testing and commissioning reports/documents should be available for the visiting Medical Physics Co-chair. Proper QA for the planning system should be done as outlined in Section 5.2.5.

5.2.4 Dry-Run Case
Participating institutions in China are required to download a dry-run case. Directions are accessible on the RTOG web site:
<http://www.rtog.org/ClinicalTrials/RTOGFoundationStudies/RTOGFoundationStudy3502.aspx>

Sites are to submit the completed case to the RTOG RTQA Center for review by the Principal Investigators. The dry-run case is a mock case provided by RTOG and should be planned exactly following the guidelines of the protocol.

5.2.5 Evaluation Criteria
A summary of the evaluation criteria and required documentation from the credentialing document (on the RTOG web site under RTOG Foundation Study 3502) is included below. The participating site needs to prepare these documents and have them ready for onsite review.

- The most recent calibration reports (less than 2 years) for primary standard ion chamber and electrometer should be submitted to visiting Medical Physics Co-Chair to review. TLDs or equivalent dosimeters comparison reports for the last 3 years (if the machine is less than 3 years old, the commissioning report and the latest calibration report will serve the purpose) for each energy in all linear accelerators used for SBRT protocol should be available for the visiting medical physics co-chair. A *Pass should be indicated* (or onsite

- measurements $\leq 5\%$).
- Criteria for Delivery System(s) QA
Follow the AAPM TG 142 Standards for SBRT/IMRT.
- Criteria for Treatment Planning QA
Each site should present all treatment planning system commissioning/acceptance/upgrade report(s) for superposition/convolution algorithm or better as described in TG 53.

All QA recommendations and acceptance criteria in TG 53 (or equivalent as judged by the visiting Medical Physics Co-Chair) should be used as the standard, including CT Houndsfield number to electronic density table. The site should also have error log books.

- Documents for Policy and Procedure/Treatment Records
Each site should have a Policy and Procedures manual, treatment record and/or chart (either in electronic or paper version), and consent form, equivalent to those developed by the American College of Radiology (ACR).
- Documents for IMRT commissioning
Each site should present acceptance testing and commissioning report as described by TG 119 or equivalent. The acceptance testing criteria for IMRT dose delivery equipment and QA protocol should follow standards as described in TG 142 or equivalent. When tracking or gating strategies are used for motion management, a moving phantom must be used for the benchmark cases described by TG 119.
- Documents for 4D and IGRT
A respiratory management procedure/sample chart should be developed to reflect that breathing motion is appropriately managed or appropriately accounted for target motion larger than 15 mm in one direction and presented to the visiting Medical Physics Co-Chair. The simulation CT system should have a QA program following AAPM TG-66 or equivalent. 4D imaging protocols and/or 3-phase 3D CT plus fluoroscopic imaging protocols should be available for inspection. The acceptable deviation from the review also should be less than 5 mm.

5.2.6 Digital RT Data Submission to RTOG Using TRIAD (6-AUG-2018)

TRIAD is the image exchange application used by the RTOG Foundation. All required digital RT planning data will be uploaded using this application. See the study-specific webpage on the RTOG website at www.rtog.org for details regarding TRIAD account and installation.

5.3 Pre-Registration Requirement: Surgeon Credentialing

Only teaching hospitals performing over 100 lung cancer surgeries each year are eligible to participate in this study.

Participating surgeons must complete and sign the credentialing form, Appendix V, prior to the institution entering any patients onto this study. The institution will e-mail the completed form to [name], Thoracic Surgery Co-Chair, at [contact] for review and approval. [name] will then e-mail the reviewed form to RTOG. Institutions should allow adequate processing time (7-10 days) before registering the first patient.

5.4 Registration

5.4.1 Summary of Procedures

This study incorporates a two-step registration process.

All patients can be registered after completing the Eligibility Checklist, STEP 1 via online registration; see the text below for online registration instructions.

All patients must be staged by FDG-PET/CT to confirm T1N0 disease. At this point, patients with confirmed T1N0 disease may be randomized.

Note: Sites must complete the Eligibility Checklist, STEP 2 via online registration for ALL patients, even for patients found not to have T1N0 disease, to indicate whether or not patients are able to continue protocol treatment and if not, to specify the reason.

Patients found not to have T1N0 disease on PET/CT will be treated off study per standard of care and will not be followed.

